- 563 • Confirm that the participant brought his/her personal insulin and regular medications.
- 564 • Participants will be asked to perform a blood ketone fingerstick. If ketones are not <0.6
565 mmol/L, study staff should treat with oral hydration and, if needed, the Glycemic
566 Treatment Guidelines will be followed; ketones will be re-checked every hour until <0.6
567 mmol/L. The participant will be able to begin participation in the camp activities once the
568 CGM reads between 80-250 mg/dL and ketones are <0.6 mmol/L.

569 **8.3.2 Assignment to Randomization Group**

570 Participants will be placed on the study CGM and insulin pump and the DiAs system implementing
571 the algorithm of the specific arm (experimental or control) will be connected to the participant's
572 CGM transmitter via Bluetooth connection. The study team will ensure the proper functioning of
573 the CGM and insulin pump.

574 **8.4 Main Admission(s) Activities and Procedures**

575 **8.4.1 General Admission(s) Overview**

576 During the entire duration of each study admission(s), the study team will remotely monitor
577 participants' real-time CGM readings. Study team members trained in all protocol interventions
578 (including the hypoglycemia and hyperglycemia safety protocols) will be with the participants at
579 all times during camp activities, with each member remotely connected to the participants CGM
580 data. In addition, a study team physician trained in all protocol and glycemic treatment guideline
581 procedures will be available at a central location on camp property.

582 All recreational activities will be managed by the staff and counsellors at Camp Holiday Trails with
583 study staff supervision.

584 During the overnight hours, study staff will be actively monitoring real-time CGM data for all
585 participants with direct access to the participants.

586 **8.4.2 Device Procedures for Participants**

587 The study insulin pump and DiAs device will be provided upon arrival to the camp. All participants
588 will continue to wear the study CGM. When participants crossover into the other treatment
589 group, they will continue to wear the same study CGM and study insulin pump with the change
590 only made to the software that the system is running.

CLINICAL PROTOCOL

591 Participants will have all equipment with them at all times. Study staff will be available at all times
592 to assure proper use of all study equipment.

593 **8.4.3 Meal Requirements**

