594 Study staff will confirm the carbohydrate content of all meals and snacks prior to entering into
595 the bolus calculator. Participants will be required to consume a minimum of 40 grams of
596 carbohydrate for each meal. All meal and correction boluses will be based on CGM readings.

597 **8.4.4 Participant's Admission(s) Itinerary**

598 Participants will generally follow the below schedule during each study admission(s).

599 **Participants will generally follow the below schedule during the 6 day/5 nigh admission:**

600 Camp Check-in (all times are estimates):

601 1300-1600: Check-in and study equipment connection. Participants will undergo the check-in
602 procedures as listed in section 8.3 and start use of study equipment.

603 1600-1800: Afternoon Camp Activity per Camp staff

604 1800: Dinner

605 1900-2030: Evening Camp Activity per Camp Staff

606 2030: Bedtime snack

607 2100-2300: Free time/Bedtime

608 Day 1 & 2

609 0800-0900: Breakfast

610 0900-1200: Morning Camp Activities. Participants will begin the activities if his/her CGM reads
611 >90 mg/dL. If ≤ 90 mg/dL, the Glycemic Treatment Guidelines will be followed until cleared to
612 begin activity. An optional morning snack will be provided between activities.

613 1230-1330: Lunch

614 1330-1500: Rest Hour

615 1500: Afternoon Snack

616 1515-1715: Afternoon Camp Activities. Participants will begin the afternoon activity if his/her
617 CGM reads >90 mg/dL. If ≤ 90 mg/dL, the Glycemic Treatment Guidelines will be followed until
618 cleared to begin activity.

619 1730-1830: Dinner

CLINICAL PROTOCOL

620 1830-2030: Evening Camp Activity per Camp Staff

621 2030: Bedtime snack

622 2100-2300: Free time/Bedtime

623 Day 3 & 4

624 Prior to breakfast on the morning of Day 3, all participants will crossover into the other treatment
625 arm. The morning and afternoon activities that the participants performed on the first and
626 second days of camp and the schedules will be identical on these days (i.e., Day 3 will be the same
627 as Day 1 and Day 4 will be the same as Day 2). Provided meals will also be similar with regards to
628 carbohydrate content.

629 Day 5

630 0800-0900: Breakfast

631

632 **Participants will generally follow the below schedule during the 4 day/3 night admission:**

633 Day 1 and Day 5 (i.e., first day of each camp admission)

634 1300-1600: Check-in and study equipment connection. Participants will undergo the check-in

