1151 Participation in the study is voluntary. Participant may withdraw at any time. For participants
1152 who do withdraw from the study, the study team will determine if their data will be used in
1153 analysis.

1154 **12.3 Confidentiality**

1155 For security and confidentiality purposes, participants will be assigned an identifier that will be
1156 used instead of their name. Protected health information gathered for this study may be shared
1157 with the third-party collaborators. De-identified participant information may also be provided to
1158 collaborators involved in the study after the appropriate research agreement has been executed.

1159 Chapter 13: Statistical Consideration

1160 13.1 Design and Randomization

1161 The study follows a double-blind randomized crossover design, comparing glycemic control
1162 obtained using the UVA HCL system – USS Virginia – alone (control) or in combination with a
1163 smart bolus calculator informed by real-time SI assessments (experimental). All study
1164 participants will undergo both treatment conditions, in different orders, defining two study arms
1165 as shown in Figure 1. Randomization (1:1) will determine whether a participant should undergo
1166 the control or experimental treatment condition first.

1167 13.2 Sample Size

1168 Sample size was determined by power analysis using G*Power 3.1 considering a paired t-test as
1169 the statistical test, comparing control group to experimental group on the primary efficacy
1170 endpoint. Effect size was determined based on the results obtained from the pilot clinical testing
1171 of the SI-informed bolus calculator in open-loop conditions to be $d_z=0.614$. A total sample size of
1172 $N=30$ subjects was obtained considering a 0.66 correlation between groups, 90% power, and
1173 $\alpha=0.05$.

1174 13.3 Outcome Measures

1175 13.3.1 Primary Efficacy Endpoint

1176 The primary endpoint will be the low blood glucose index (LBGI) computed from CGM collected
1177 in the four hours following the dinner meal.

1178 13.3.2 Secondary Outcomes

1179 Secondary endpoints will include analysis over four different time intervals:

- 1180 1. the dinner postprandial period (i.e., the four hours following dinner)
- 1181 2. daytime, i.e., breakfast to bedtime
- 1182 3. nighttime, i.e., bedtime to breakfast
- 1183 4. 24 hours

1184

1185 The glycemic outcomes computed over the four horizons will be:

- 1186 • percentage of time spent below 70 mg/dL

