- 1187 • percentage of time spent in 70-140 and 70-180 mg/dL
- 1188 • percentage of time spent above 180 and 250 mg/dL
- 1189 • the high blood glucose index

CLINICAL PROTOCOL

- 1190 • average CGM
- 1191 • CGM coefficient of variation
- 1192 • Total number and amount of carbohydrate administered as rescue treatments

1193 All glycemic outcomes (primary efficacy endpoint and secondary outcomes) will be computed
1194 based on CGM records. The primary analysis will focus on the postprandial period, but other
1195 analyses will evaluate different time intervals to assess whether the impact on the postprandial
1196 period will be influential enough to impact the overall daily control. Paired t-tests or non-
1197 parametric Wilcoxon signed-rank tests will be used to compare the control and experimental
1198 arms on the different glycemic outcomes, in case of normally/non-normally distributed samples
1199 respectively (Shapiro-Wilk test). Significance level will be set at a P value less than 0.05. All
1200 statistical analyses will be computed in SPSS Statistics 26 (IBM).

1201 **13.4 Safety Analyses**

1202 Safety endpoints are secondary outcomes addressing hypoglycemia and hyperglycemia, i.e.,
1203 percentage of time below 70 mg/dL and above 250 mg/dL, and total number and amount of
1204 carbohydrate administered as rescue treatments.

1205 **13.5 Baseline Descriptive Statistics**

1206 Baseline demographic and clinical characteristics of the cohort of all randomized participants will
1207 be summarized in a table using summary statistics appropriate to the distribution of each
1208 variable. Descriptive statistics will be displayed overall and by treatment group.

1209 Will include:

- 1210 • Age
- 1211 • HbA1c
- 1212 • Gender
- 1213 • Race/ethnicity
- 1214 • Diabetes duration
- 1215 • BMI

1216 **13.6 Device Issues**

1217 The following tabulations and analyses will be performed by treatment group to assess device
1218 issues:

- 1219 • Device malfunctions requiring study team contact and other reported device issues

CLINICAL PROTOCOL

- 1220 • Sensor performance metrics (difference, absolute relative difference, and
1221 International Organization for Standardization criteria) – if applicable, by sensor
1222 version.
- 1223 • % time CGM data available - overall and by month
- 1224 The following tabulations will be performed for the Experimental arm only:
- 1225 • Performance metrics, describing the CLC system and its components like:

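### If the 6 day/5 night camp is run, rescue carbohydrate is listed as an unscaled total although the first system has three dinner and night windows and the second has two; define it per window and define the 24-hour unit

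*Combined protocol and SAP*

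**What the plan says.** Section 1.3 allows either one 6 day/5 night camp or two 4 day/3 night weekends. In the 6-day itinerary (section 8.4.4), equipment is connected between 1300 and 1600 on an unnumbered check-in day, and dinner is at 1800. Section 8.3.2 confirms that what is connected is already arm-specific: "the algorithm of the specific arm (experimental or control) will be connected to the participant's" transmitter. Days 1 and 2 follow. Then "Prior to breakfast on the morning of Day 3, all participants will crossover into the other treatment" arm. Days 3 and 4 repeat the activities of Days 1 and 2, with similar meals. Day 5 lists only breakfast, and section 8.5 puts discharge at about 0900-1200.

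Section 13.3.2 names four horizons, including "the dinner postprandial period (i.e., the four hours following dinner") and "nighttime, i.e., bedtime to breakfast". Daytime is also defined. The 24-hour horizon is named with no start or end. Under "The glycemic outcomes computed over the four horizons will be", the list includes "Total number and amount of carbohydrate administered as rescue treatments". Section 13.4 takes the same total as a safety endpoint. For the test, paired t-tests or non-"parametric Wilcoxon signed-rank tests will be used to compare the control and experimental" arms, the choice depending on Shapiro-Wilk. The plan includes no period or sequence term.

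**The concern.** A total grows with the time over which it is collected. In the 6-day format that time differs between a participant's two systems, and which system gets more of it depends on randomised order. The other listed outcomes (LBGI, high blood glucose index, percentages of time, mean CGM, coefficient of variation) do not grow with exposure and are not part of this point.

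Two things are at stake. First, if totals are summed over each system's use, part of each paired difference reflects only which system came first. The planned tests treat that part as noise. Second, each arm's mean total would mix participants with three windows and participants with two (2.5 on average at equal order), so a reader could not convert it to a rate. Rescue carbohydrate is a named safety endpoint in a trial whose primary aim (section 1.5) is safety and feasibility, so its unit should be clear.

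**Working it through.** **The plan's own figure.** A paired t-test with dz = 0.614 and two-sided alpha 0.05 reaches 90% power at N = 30 (power 0.901), as section 13.2 states. That calculation sizes the primary endpoint only, and this point does not depend on it.

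**Exposure, 6-day format** (sections 8.4.4 and 8.5, taking breakfast as 0800).
- First system: from 1300-1600 on the check-in day to 0800 on Day 3 = 3 × 24 − 5 = 67 h down to 3 × 24 − 8 = 64 h. Dinners and nights: check-in day, Day 1, Day 2 = 3 of each.
- Second system: from 0800 on Day 3 to 0900-1200 on Day 5 = 49 to 52 h. Dinners and nights: Days 3 and 4 = 2 of each.
- Check: 3 + 2 = 5 nights, as the format's name says.
- Two-weekend format: 3 dinners and 3 nights per system, so it is balanced.

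**24-hour units.** Complete units per system are 2 and 2 if counted breakfast to breakfast, but 2 and 1 if counted midnight to midnight or dinner to dinner. The missing definition therefore decides which data enter.

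**Effect of summing 3 against 2 windows with no treatment effect.** Let a participant have λ rescues per window, with mean m (assumed gamma, shape 4) and Poisson counts. The difference in totals has mean +λ if the experimental system comes first and −λ if it comes second, with Poisson variance 5λ.
- Variance seen by the paired test: E(λ²) + 5m = 1.25m² + 5m.
- Share due to unequal exposure: 1.25m² / (1.25m² + 5m). At m = 0.25, 0.5, 1 and 1.5 this is 6, 11, 20 and 27%.
- At a 15/15 split the mean shift is zero, and the true variance per participant behind the mean difference is only 0.25m² + 5m. At m = 1 the ratio is 5.25/6.25 = 0.84. The null rejection rate is then about P(|Z| > 1.96/√0.84 = 2.14) = 3.2%, against a nominal 5%.

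**Simulation.** N = 30, 15/15, the plan's Shapiro-Wilk rule, and an assumed 30% reduction for power. Ranges are across repeated runs.

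| Assumed rescues per window | Power, totals | Power, per window | Null rejection, totals | Null rejection, per window |
|---|---|---|---|---|
| 0.25 | 14-15% | 15% | 4.1% | 4.4-4.6% |
| 0.5 | 23-24% | 25-26% | 4.0-4.1% | 5.2-5.5% |
| 1 | 39-40% | 44-47% | 3.2-3.3% | 4.9-5.3% |
| 1.5 | 53% | 62-63% | 2.6-3.1% | 5.1-5.3% |

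**Which rows are plausible.** The documents give no rescue rate. If one assumes 2 rescues per 24 h spread evenly, a 4-hour dinner window has 2 × 4/24 = 0.33. A night of 9-11 h (bedtime 2100-2300 to 0800) has 0.75-0.92. With evening and night hours weighted 2.5 to 1, the dinner figure is about 0.42. Simulated power at 0.33 was 17.4% (totals) against 18.0% (per window), and at 0.42 it was 20.4% against 22.8%. At the night rates the loss is roughly 4-6 points.

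**24-hour horizon.** At 2 rescues per 24 h and 64 against 52 h of use, power for totals against per-24-h rates was 71 vs 73% (even rate), 68 vs 75% (evening and night heavy) and 74 vs 69% (daytime heavy, 4 to 1). Scaling by time can therefore help or hurt slightly.

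**The case against.** The strongest reply is that no section says windows are summed across days. Section 13.3.2 words its horizons in the singular, and two have fixed lengths (four hours, 24 hours). A total within one such window is already scaled. This stands: a reader might infer that the plan prescribes a 3-against-2 sum, and the text does not support that as fact. What it supports is that the outcome is a total, no scaling is stated, and nothing says how several windows become one value per participant. Summing is one open reading, and the losses above are conditional on it.

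The matched Days 1-2 and 3-4 might also suggest that the check-in evening is left out. That is reasonable, but unstated.

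On scope, section 13.1 refers to Figure 1, which shows the two-weekend case. The point is moot if that format is used. The 6-day format remains permitted, so the definition should work for both.

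On weight, the outcome is secondary with no power target, and power is low by either method. That also stands.

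A reader might further infer that the imbalance favours one system or raises the false-positive rate. It follows period, not treatment, so it cancels in the mean at equal order. Inflation needs a markedly unequal split: a separate simulation gave 6.1-8.4% at 20/10 for assumed rates of 0.3-1.0. Chapter 4 specifies blocked randomisation and allows dropouts to be replaced. If 30 are analysed after random loss from equal groups, a split of 20/10 or worse cannot occur from 36 randomised (18 + 18), and has probability 0.04% from 40 and 0.9% from 50.

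**Conclusion.** The point holds as a minor one, for the 6 day/5 night format only. The 3-against-2 window count follows directly from the itinerary, and the missing scaling, combination rule and 24-hour definition are plain in sections 13.3.2 and 13.4. If totals are summed, the paired test is conservative (about 3-4% under the null). It loses roughly 1-2 points of power at 0.25-0.5 rescues per window and 4-9 points at 0.8-1.5. The larger loss is more plausible for nights than for dinners. The reported arm means would also lack a clear time base.

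These sizes rest on assumed rates, an assumed 30% reduction and a Poisson-gamma model. Grams were not simulated. The documents do not support a claim of bias between systems, of false-positive inflation, or of any effect on the primary LBGI endpoint through this route.

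**What to change.** In section 13.3.2, and so in 13.4:

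1. Analyse rescue number and grams as the mean per window for the dinner, daytime and night horizons. In the two-weekend format this divides both systems' dinner and night totals by three and changes nothing.
2. For the 24-hour horizon, choose one unit in advance as the main analysis and keep the other as a sensitivity analysis: breakfast to breakfast on the matched days (Days 1-2 against Days 3-4, 48 h each), or per 24 h of system use. Matched days compare like with like whatever the time of day of rescues, but they discard the check-in evening. In a paired-t grid at 1-3 rescues per 24 h they had 1-9 points less power than per-24-h rates. Two of that grid's three exposure settings ended second-system use at 0800 on Day 5, so the range is approximate.
3. State how check-in-evening and Day 5 hours are handled in each horizon.

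The cost is a few sentences of wording and a small change in power, in either direction, for the 24-hour horizon. No extra data, visits or participants are needed. The itinerary and the primary endpoint stay as they are.

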1.6 Secondary Specific Aim

- Demonstrate that the use of the SI-informed smart bolus calculator in an HCL system provides increased protection against hypoglycemia.

229 **Chapter 2: Study Devices**

230 **2.1 Insulin Pump**

231 The study system will include the Tandem t:ap research pump connected to the UVA DiAs system
232 running on a dedicated external smartphone, implementing either the USS Virginia algorithm
233 alone or the USS Virginia algorithm with the smart bolus calculator.

234 **2.2 Continuous Glucose Monitor**

235 The study CGM will include Dexcom G6 transmitter and sensors. The CGM sensor is viable for 10
236 days. Like the insulin pump, the CGM system will be connected to DiAs.

237 **2.3 Blood Glucose Meter and Strips**

238 Upon need, blood glucose levels will be measured using the study blood glucose meter
239 (glucometer). The CGM device will be calibrated, if needed, using the study glucometer and strips
240 in accordance with the manufacturer's labeling. Glucometers will be available during the study
241 admission(s).

242 **2.4 Ketone Meter and Strips**

243 Upon need, blood ketone levels will be measured using the Abbott Precision Xtra meters and
244 strips in accordance with the manufacturer's labeling. The blood glucose meter component of
245 the Precision Xtra Device will not be used. Ketone meters will be available during the study
246 admission(s).

247 **2.5 Study Devices Accountability Procedures**

248 Device serial numbers will be recorded, and use of equipment will be tracked.

249 **Chapter 3: Study Screening**

250 **3.1 Participant Recruitment and Enrollment**

251 Participants will be recruited from the UVA Center for Diabetes Technology registry, social media
252 advertisements, physician contacts at pediatric diabetes clinics in Virginia, and previous camp
253 attendance data. The enrollment goal in the pilot study will be to complete up to three
254 participants. Up to four participants may sign consent/assent forms. The enrollment goal for the
255 main study is to complete 30 participants. Up to 70 participants may sign the consent form.

256 **3.2 Informed Consent and Authorization Procedures**

257 Before consent has been obtained, participants will be asked inclusion/exclusion criteria
258 questions during prescreening to determine study eligibility. Before completing any procedures
259 or collecting any data that are not part of usual care, written informed consent will be obtained.

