377 Screening procedures will last approximately 1-2 hours. Screening can be performed via
378 videoconference. Once all results of the screening evaluations are available, a decision will be
379 made to determine the participant's eligibility for the study or if one or more part of the screening
380 will have to be repeated. If at the first screening or repeat screening an exclusionary condition is
381 identified, the participant will be excluded from participation with follow up and referred to their

CLINICAL PROTOCOL

382 primary care physician as needed. The study physician may elect to rescreen participants if their
383 clinical situation changes.

384 **Chapter 4: Randomization Visit**

385 Once eligibility is met, the participant may continue with randomization at the conclusion of the
386 screening appointment. Using a randomized block design, the participants will be randomly
387 assigned to either one of the two treatment groups. Screening failures and study dropout
388 participants may be replaced.

389 **4.1 Pilot Participants**

390 Participants will not be randomized in the Pilot Study.

391 **4.2 Main Study Participants**

392 Approximately 30 participants will be randomized 1:1 to use USS Virginia or USS Virginia with SI-
393 informed bolus calculator first. Up to 70 participants may sign the informed consent form.

394 **Chapter 5: Study Equipment Training**

395 Participants will be trained on the use of the study CGM after study eligibility has been met.
396 Additional equipment training may begin at arrival to study admission(s) after the system
397 equipment has been put in place. The purpose of this training is to introduce the study insulin
398 pump and study CGM to the participant.

399 **5.1 CGM Training**

400 A study CGM will be provided to all participants after meeting study eligibility. The participants
401 will be provided with CGM equipment and instructed to place the study CGM ~24-48 hours prior
402 to arrival to camp and use the study CGM on a daily basis. If the participant has prior use of the
403 CGM, re-training will be specific to the individual. The study team will have participants who are
404 not familiar with the study CGM watch the Dexcom online training videos
405 (<https://www.dexcom.com/training-videos>). Study staff will specifically identify how alarms are
406 set using the app and the frequency that these alarms repeat. Parents may optionally use the

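### Section 13.3.2 analyses a randomised two-sequence crossover with no period term; a period-adjusted primary test is a cheap improvement, although the planned test is not shown to be invalid

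*Combined protocol and SAP*

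**What the plan says.** Section 13.1 describes a double-blind crossover in which order is randomised: "Randomization (1:1) will determine whether a participant should undergo" the control or the experimental condition first. Chapter 4 adds blocking ("Using a randomized block design, the participants will be randomly" assigned) and makes replacement of dropouts optional.

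Section 13.2 sizes the trial for a paired comparison: "Sample size was determined by power analysis using G*Power 3.1 considering a paired t-test as" the test, with dz = 0.614, 90% power, alpha 0.05 and N = 30.

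The last paragraph of Section 13.3.2 covers the primary LBGI and all secondary outcomes. Paired t-tests are used for normal data; otherwise non-"parametric Wilcoxon signed-rank tests will be used to compare the control and experimental" arms, with Shapiro-Wilk deciding. Chapter 13 mentions no period or sequence term and no confidence interval.

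Two other places bear on whether the sequences finish equal. Section 3.1 sets a target of completers (the goal for the "main study is to complete 30 participants. Up to 70 participants may sign the consent form"). Section 12.2 leaves open whether partial data count: for participants "who do withdraw from the study, the study team will determine if their data will be used in" the analysis.

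**The concern.** In a two-sequence crossover, a change between the first and second period that is common to everyone enters each experimental-minus-control difference with a sign fixed by sequence. It is added for participants who have the experimental system second and subtracted for those who have it first. A one-sample test on the pooled differences treats that spread as noise, although the randomised order would let it be removed. At equal sequences the result is lost power and a wider interval. At unequal sequences part of the shift also stays in the estimated effect.

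The 6-day itinerary in Section 8.4.4 gives a concrete reason to expect that the periods may differ. The switch comes before breakfast on Day 3, without a washout. The check-in evening and its dinner fall only in the first period, so there are three dinners before the switch (check-in, Day 1, Day 2) and two after it (Day 3, Day 4). The primary endpoint is measured after dinner.

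**Working it through.** **Inputs.** N = 30, dz = 0.614, 90% power and alpha 0.05 come from Section 13.2; 1:1 order comes from Section 13.1. The size of the period shift is not in the documents. It is assumed here, and expressed in SDs of the paired difference.

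**The plan's own figure.** Paired t-test, noncentrality 0.614 × √30 = 3.363, 29 df, two-sided 0.05: power 0.9014 (0.8909 at N = 29). N = 30 reproduces. The plan does not state sidedness; a one-sided test would give N = 25.

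**Model.** Paired difference = effect + p × (+1 or −1 by sequence) + error of SD 1, where p is the shift and n1, n2 are the sequence sizes.

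- Planned t-test: the estimate has mean effect + p × (n1 − n2)/N. The sum of squares is noncentral chi-square with 29 df and noncentrality 4·n1·n2·p²/N, which is 30p² at 15/15.
- Adjusted test: half the difference between sequence means of period 2 minus period 1. Its SE is √((1/n1 + 1/n2)/4) with 28 df, and p cancels. At 15/15 the SE is 0.1826 and power is 0.9007; power is 0.8995 at 16/14 and 0.8956 at 17/13.

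**Equal sequences (15/15), t-test.**

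| Shift p | Planned power | Adjusted power | Planned type I error | Planned 95% half-width | Adjusted half-width |
|---|---|---|---|---|---|
| 0 | 90.1% | 90.1% | 5.0% | 0.370 | 0.371 |
| 0.25 | 89.0% | 90.1% | 4.4% | 0.382 | 0.371 |
| 0.5 | 85.2% | 90.1% | 2.9% | 0.415 | 0.371 |

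The two powers are equal at p = 0.062, and the two half-widths at p = 0.049. A 1-point loss of power needs p = 0.24; a 2-point loss needs p = 0.33.

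A simulation of the signed-rank test at 15/15 (40,000 trials) behaves alike: power 89.2%, 87.7% and 83.0% at the three shifts, and type I error 4.9%, 4.3% and 2.8%.

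**Unequal sequences.** At 17/13, (n1 − n2)/N = 4/30 = 0.133. The conditional bias is 0.133 × 0.25 = 0.033 SD, or 0.033/0.614 = 5% of the planned effect. At p = 0.5 it is 0.067 SD, or 11%. Planned power at p = 0.5 is then 92% or 76%, depending on the sign of the shift, against 89.6% adjusted.

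Type I error of the planned t-test:

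| Split | p = 0.25 | p = 0.5 | p = 1 |
|---|---|---|---|
| 16/14 | 4.4% | 3.1% | 0.9% |
| 17/13 | 4.7% | 3.9% | 2.1% |
| 18/12 | 5.1% | 5.3% | 4.6% |
| 19/11 | 5.7% | 7.3% | 9.4% |

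**The case against.** The strongest reply is that no period shift is documented and the design works against one. Section 1.3 keeps meals and activities similar under both systems. Section 8.4.4 repeats Days 1 and 2 as Days 3 and 4. The two-weekend format has about a week of washout and three dinners in each admission. Blocking, possible replacement and the goal of 30 completers make a badly unequal split unlikely, and if dropout is unrelated to sequence the conditional bias averages to zero over randomisation. The SD behind dz may also already contain a shift. In that case planned power stays at 90%, and adjustment would raise it to about 92% (p = 0.25) or 95% (p = 0.5). All of this stands. It makes the point an improvement and not a defect, but it does not supply the missing term.

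Three stronger readings are tempting and are not supported.

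- A reader might infer that the planned test is invalid. With equal or nearly equal sequences it is valid or conservative; excess type I error needs both a split of 18/12 or worse and a real shift.
- A reader might take a shift of about 0.05 SD as the point where power suffers. That is only where the interval widths cross. Any nonzero shift enters the error, and the loss near the crossing is negligible.
- A reader might infer an actual shift from the expected fluctuations in insulin sensitivity (Section 1.2) or from pump settings that may be changed at any time (Section 5.2.3). Fluctuation is not drift across days. Individual changes need not move everyone the same way, and a period term removes only their average.

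**Conclusion.** The omission is real: order is randomised and then not used in the analysis. Its cost depends on a shift that the documents do not quantify. Under the model above at 15/15, the planned t-test loses about 1 point of power at 0.25 SD and about 5 points at 0.5 SD, and its interval is 3% and 12% wider. Below about 0.06 SD adjustment gains no power. Control of type I error is secure up to about 17/13. At 18/12 it reaches about 5.3%, and at 19/11 about 9.4%, for shifts up to 1 SD. Such splits are not expected, but optional replacement and the discretion in Section 12.2 do not exclude them. These figures assume normal errors and a shift common to all participants. The change is worth making because it is cheap, not because the planned analysis is shown to fail.

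**What to change.** In Section 13.3.2, pre-specify a period-adjusted primary analysis: a two-sample t-test, between randomised sequences, of each participant's period 2 minus period 1 LBGI. Report half the difference in sequence means as the treatment effect, signed as experimental minus control, with its 95% CI. Apply Shapiro-Wilk to these differences after centring within sequence; if they are non-normal, use the rank-sum test of the same differences between sequences. Apply the same rule to the secondary outcomes. Section 1.3 presents the two camp formats as alternatives, so add a format term only if both are actually run.

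The cost is wording and one degree of freedom. With no shift, t-test power goes from 90.14% to 90.07% at 15/15 and is about 0.6 point lower at 17/13. In simulation with no shift, the rank branch loses about 1.3 points with normal data, and the whole two-step rule about 1.6 points under an assumed heavy-tailed shape. N stays at 30. The change does not address carryover in the format without a washout.
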